**Additional criteria for Part 2 - Dose Expansion subjects**

**114. MM subjects only**

- Pathologically documented, definitively diagnosed, relapsed or refractory disease following at least 3 lines of therapy including but not limited to a proteasome inhibitor, an immunomodulatory agent and/or CD38-targeted immunochemotherapy.

**NOTE:** The investigator must be of the opinion that no other treatment option will result in a durable response.

**115. NHL subjects only**

- Pathologically confirmed DLBCL that has demonstrated clinical or radiographic progression on at least two prior therapies

**NOTE:** For subjects with refractory disease and who have received radiotherapy, PET positivity should be demonstrated no less than 6 weeks after the last dose of radiotherapy.

**116. AML subjects only**

- Pathologically confirmed diagnosis of AML as defined by the WHO Classification ([Appendix H](#)) persisting or recurring following no more than 2 lines of prior therapies

**4.2 Exclusion Criteria**

201. Previously received an allogeneic stem cell transplant within 6 months of study day 1 OR having signs or symptoms of acute or chronic graft-versus-host disease
202. Autologous stem cell transplant < 90 days prior to study day 1
203. Candidates for stem cell transplant should have failed or are not considered eligible for either allogeneic and autologous transplant

204. History of other malignancy except:
- Malignancy treated with curative intent and with no known active disease present for  $\geq 2$  years before enrollment and felt to be at low risk for recurrence by the treating physician
  - Adequately treated non-melanoma skin cancer or lentigo maligna without evidence of disease
  - Adequately treated cervical carcinoma in situ without evidence of disease
  - Adequately treated breast ductal carcinoma in situ without evidence of disease
  - Prostatic intraepithelial neoplasia without evidence of prostate cancer
  - Adequately treated urothelial papillary noninvasive carcinoma or carcinoma in situ
205. Myocardial infarction within 6 months of study day 1
206. Symptomatic congestive heart failure (New York Heart Association > Class II) ([Appendix F](#))
207. History of arterial thrombosis (eg, stroke or transient ischemic attack) in the past 6 months prior to study day 1
208. Uncontrolled active infection requiring intravenous anti-infective treatments within 1 week of study day 1
209. Known positive results for human immunodeficiency virus (HIV)
210. Active hepatitis B and C based on the following results:
- Positive for hepatitis B surface antigen (HBsAg) (indicative of chronic hepatitis B or recent acute hepatitis B).
  - Negative HBsAg and positive for hepatitis B core antibody: hepatitis B virus DNA by polymerase chain reaction (PCR) is necessary. Detectable hepatitis B virus DNA suggests occult hepatitis B.
  - Positive Hepatitis C virus antibody (HCVAb): hepatitis C virus RNA by PCR is necessary. Detectable hepatitis C virus RNA suggests chronic hepatitis C
211. Unresolved toxicities from prior anti-tumor therapy, defined as not having resolved to Common Terminology Criteria for Adverse Events (CTCAE) version 4.03 grade 1, or to levels dictated in the eligibility criteria with the exception of grade 2 peripheral neuropathy, alopecia or toxicities from prior anti-tumor therapy that are considered irreversible (defined as having been present and stable for > 4 weeks prior to study day 1 may be allowed if they are not otherwise described in the exclusion criteria AND there is agreement to allow by both the investigator and sponsor)
212. Antitumor therapy (chemotherapy, antibody therapy, molecular-targeted therapy, retinoid therapy, or investigational agent or procedures) within 14 days of day 1.
213. Prior systemic radiation therapy must have been completed at least 28 days before study day 1. Prior focal radiotherapy completed at 14 days before study day 1.

Approved

214. Males and females of reproductive potential who are unwilling to practice an acceptable method(s) of effective birth control while on study through 3 months after receiving the last dose of study drug. Acceptable methods of effective birth control include sexual abstinence (males, females); vasectomy; bilateral tubal ligation/occlusion; or a condom with spermicide (men) in combination with barrier methods (diaphragm, cervical cap, or cervical sponge), hormonal birth control or IUD (females).

**NOTE:** A woman is considered of childbearing potential (WOCBP), (ie, fertile) following menarche and until becoming post-menopausal unless permanently sterile. Permanent sterilization methods include hysterectomy, bilateral salpingectomy and bilateral oophorectomy.

- A postmenopausal state is defined as no menses for 12 months without an alternative medical cause. A high follicle stimulating hormone (FSH) level in the postmenopausal range may be used to confirm a post-menopausal state in women not using hormonal contraception or hormonal replacement therapy. However, in the absence of 12 months of amenorrhea, a single FSH measurement is insufficient.

215. Females who are lactating/breastfeeding or who plan to breastfeed while on study through 3 months after receiving the last dose of study drug.
216. Females with a positive pregnancy test or planning to become pregnant while on study through 3 months after receiving the last dose of study drug.
217. Males who are unwilling to abstain from sperm donation while on study through 3 months after receiving the last dose of study drug.
218. History or evidence of any other clinically significant disorder, condition or disease that, in the opinion of the investigator or Amgen physician, if consulted, would pose a risk to subject safety or interfere with the study evaluation, procedures or completion.
219. Use of any over-the-counter or prescription medications within 14 days or 5 half-lives (whichever is longer), prior to study day 1 that was not reviewed and approved by the principal investigator and the Amgen medical monitor
220. Use of herbal medicines (eg, St. John's wort), vitamins, and supplements consumed by the subject within 14 days prior to study day 1 that was not reviewed and approved by the principal investigator and the Amgen medical monitor
221. Use of any known inhibitors of P-gp within 14 days or 5 half-lives (whichever is longer) or grapefruit juice or grapefruit containing products within 7 days prior to study day 1 that was not reviewed and approved by the principal investigator and the Amgen medical monitor
222. Use of known cytochrome P450 (CYP) 3A4 sensitive substrates, (**with a narrow therapeutic window**), within 14 days or 5 half-lives (whichever is longer) of the drug or its major active metabolite, whichever is longer, prior to study day 1 that was not reviewed and approved by the principal investigator and the Amgen medical monitor

Approved

223. Use of known P-gp substrates (**with a narrow therapeutic window**) within 14 days or 5 half-lives (whichever is longer) prior to study day 1 that was not reviewed and approved by the principal investigator and the Amgen medical monitor
224. Subject likely to not be available to complete all protocol-required study visits or procedures, and/or to comply with all required study procedures (eg, long term follow-up) to the best of the subject and investigator's knowledge
225. Known sensitivity to any of the products or component to be administered during dosing

**226. MM subjects with any of the following criteria are excluded:**

- Multiple myeloma with IgM subtype
- POEMS syndrome (polyneuropathy, organomegaly, endocrinopathy, monoclonal protein, and skin changes)
- Existing plasma cell leukemia
- Waldenstrom's macroglobulinemia
- Amyloidosis

**227. NHL subjects with the following criteria are excluded:**

- CNS lymphoma or evidence of uncontrolled CNS disease
- Burkitt's lymphoma
- Lymphoblastic lymphoma

**228. AML subjects with any of the following criteria are excluded:**

- Circulating white blood cells > 25,000 / $\mu$ l. Hydroxyurea to control peripheral blood leukemic cell counts, within 24 hours of study day 1 is permitted.
- Promyelocytic leukemia

## **5. SUBJECT ENROLLMENT**

Before subjects begin participation in any study-specific activities/procedures, Amgen requires a copy of the site's written institutional review board/independent ethics committee (IRB/IEC) approval of the protocol, informed consent form, and all other subject information and/or recruitment material, if applicable (see [Section 11.2](#)). All subjects must personally sign and date the informed consent form before commencement of study-specific activities/procedures.

A subject is considered enrolled when they have met all eligibility criteria, including completing any pre-treatment safety assessment(s) prior to initial dosing on day 1. The Investigator is to document the enrollment decision and date, in the subject's medical record and in/on the enrollment eCRF.

An Amgen representative will notify the sites in writing when a cohort is open to screen new subjects. Each subject who enters into the screening period for the study (defined as the point at which the subject signs the informed consent) receives a unique subject identification number before any study procedures are performed. The subject identification number will be assigned manually. This number will be used to identify the subject throughout the clinical study and must be used on all study documentation related to that subject. The unique number will consist of 11 digits: digits 1 to 3 represent the last 3 digits of the protocol (eg, 173), digits 4 to 8 the country code and site number, digits 9 to 11 the subject number at the site.

Subjects who fail to meet the eligibility criteria will be allowed to rescreen once with agreement between the Amgen Medical Monitor and PI. Re-screened subjects must perform all qualifying assessments required for eligibility, including reconsenting the subject, within 21 days of their D1 visit. The subject identification number, assigned during the original screening period must remain constant throughout the entire clinical study if a subject is rescreened.

#### **5.1 Treatment Assignment**

An Amgen representative will notify the site(s) in writing when a dose cohort/group (dose escalation part) or the dose expansion part, respectively, are open to screen and enroll new subjects. The notification will include the cohort/group and dose level in which subjects will be enrolled. The treatment assignment date is to be documented in the subject's medical record and on the enrollment eCRF.

### **6. TREATMENT PROCEDURES**

#### **6.1 Classification of Product**

The Amgen Investigational Product used in this study is AMG 397.

The Investigational Product Instruction Manual (IPIM), a document external to this protocol, contains detailed information regarding the storage, preparation, destruction, and administration of AMG 397.

#### **6.2 Investigational Product**

##### **6.2.1 Amgen Investigational Product AMG 397**

AMG 397 is an oral MCL1 inhibiting agent. AMG 397 will be manufactured and packaged by Amgen Inc. and distributed using Amgen clinical study drug distribution procedures. AMG 397 will be provided as 5 mg, 20 mg, and 100 mg tablets, and will be packaged in bottles of 15 tablets.

AMG 397 will be dispensed and administered at the research facility by qualified staff member(s).

#### **6.2.1.1 Dosage, Administration, and Schedule**

During dose escalation (Part 1), AMG 397 will be given orally once daily for 2 consecutive days followed by 5 days break at a weekly interval, as part of a 28-day treatment cycle. [Table 3](#) shows the planned dose levels for dose escalation.

During dose expansion (Part 2) AMG 397 will be given orally once daily for 2 consecutive days followed by 5 days break at a weekly interval, as part of a 28-day treatment cycle. The planned dose level(s) for dose expansion will be determined based on data collected during dose escalation.

On days of hospitalization and during clinic visits, doses will be administered at the clinic. Subjects will self-administer AMG 397 on all other designated timepoints per [Table 4](#) and [Table 5](#) on days without clinic visits.

AMG 397 can be taken with or without food (ie, subjects may choose to eat prior to or after taking study drug). The tablet should be swallowed whole without crushing or breaking. No tablet should be ingested if it is broken, cracked, or otherwise not intact.

Subjects will be asked to record the date, time, and number of tablets consumed in a subject drug diary that must be brought to each study visit and will be reviewed by study staff. The amount dosed, lot number of IP, and start date will be recorded on each subject's eCRF(s).

The amount dispensed, amount returned, date dispensed, date returned, and lot number of AMG 397 are to be recorded in the site's drug accountability log for each subject. Please refer to the Investigational Product Instructional Manual for more details on dosage, administration and schedule of AMG 397.

If a subject develops a reaction, subjects should acutely be treated according to best clinical practice. Medication may be administered as deemed appropriate by the investigator to control any reactions according to best clinical practice. Increase monitoring of vital signs as medically indicated until the subject is deemed medically stable in the opinion of the investigator. All medication and symptoms should be documented in the eCRF. Amgen must be notified within 24 hours when a subject has had  $\geq$  Grade 3 AE.

The effects of overdose of this product are not known.

#### 6.2.1.1.1 Lead-in Dosing

There is a potential for tumor lysis syndrome (TLS) in subjects affected by hematologic malignancies especially in those with bulky disease, elevated pretreatment lactate dehydrogenase (LDH) levels, elevated leukocyte count, renal dysfunction, and dehydration. To mitigate the risk of TLS, tumor lysis syndrome prophylaxis must be initiated in all subjects prior to the first dose of AMG 397 and prior to any dose escalation ([Section 6.5.7](#)).

Additionally, when an event meeting clinical or laboratory TLS per Cairo-Bishop criteria ([Appendix K](#) and [Appendix L](#)) is observed, lead-in dosing may be initiated to evaluate a step-wise dose escalation for all subsequent dosing. See [Figure 2](#) for an example of lead-in dosing. .

The DLRT will convene to review the safety data and may determine a lead-in dose, which will not exceed the dose where the TLS was observed. Once TLS criteria is resolved, this lead-in dose will be administered for the first week of dosing (cycle 1 week 1). Upon completion of the lead-in dosing period, subject(s) will receive their designated target dose level of AMG 397 per [Table 3](#) beginning on the second week of dosing (cycle 1 week 2) and all subsequent dosing.

**NOTE:** Once lead-in dosing is implemented, a maximum of 50% dose escalation of AMG 397 will be imposed between dose cohort levels per [Table 3](#) for the target dose.

Once lead-in dosing is initiated, additional monitoring of electrolyte values is required prior to dosing at the following times (see [Table 4](#) and [Table 5](#)):

- Prior to the Week 1, Day 1 Dose
- Prior to each dose during the Lead-in Period
- Prior to the initial dosing at the target dose level

Prior to administering AMG 397, all electrolyte values (ie, potassium, uric acid, inorganic phosphorus, calcium) must be within normal range.

**NOTE:** Laboratory value changes must be confirmed by another laboratory test (1-2 hours later) prior to assigning a TLS grade.

#### Dose Adjustments for Lead-In Dosing

Evidence of TLS will be carefully monitored on study and AMG 397 will be held until resolution of TLS abnormalities. Following lead-in dosing of AMG 397, if one or more

Cairo-Bishop criteria is met (See [Appendix K](#) and [Appendix L](#)), no additional AMG 397 doses will be administered until it is resolved (eg, laboratory values are no longer within range of the values stated in [Appendix K](#) and [Appendix L](#)). Upon resolution, the subject will repeat the lead-in dosing for an additional week prior to receiving the target dose.

**NOTE:** Lead-in dosing will be repeated if the subject is observed to meet one or more of the Cairo-Bishop criteria post-dose.

Decisions to modify the AMG 397 lead-in dosing period regimen, lead-in period starting dose, and dosing increments, will be made in conjunction with the investigator and Amgen medical monitor and communicated to the IRB/EC, as appropriate.

#### **6.2.1.2 Dose-cohort Study Escalation and Stopping Rules**

The Dose Level Review Team (DLRT) will convene before decisions to dose escalate or de-escalate is made or when cohorts are suspended per protocol. The DLRT will be composed of select Investigator(s), Amgen medical monitor, Amgen Global Safety Officer or designee, Amgen Clinical Research Study Manager (CRSM) and Biostatistics representative or designee. Additional members may be added as needed (eg, clinical pharmacologist). The DLRT voting members include the Amgen Medical Monitor and Global Safety Officer or designee, in consultation with the investigator(s) or designee. The DLRT members are responsible for dosing decisions, which may include escalation to the next nominal or intermediate dose, de-escalation to a lower nominal or intermediate dose; alternative dose frequencies, continuation, delay or termination of dosing; or repetition or expansion of a cohort; implementation of lead-in dosing, or determination of RP2D. See [Section 3.1](#) for more details regarding the study design and the dose escalation plan for this study.

The DLT-observation period is defined as, at minimum, 28 days after the initial dose of AMG 397. Once lead-in dosing period is initiated, the DLT-observation period is defined as the amount of time for subject(s) for each dose cohort to receive at least 1 week of lead-in dose and 3 weeks of target dose.

A subject is deemed DLT-evaluable if during the DLT-observation period the subject met at least one of the following criteria:

- Received at least 75% of the planned dose of AMG 397
- Experienced a DLT

Available study data, including data collected after the initial DLT-observation period along with demographics, IP administration, medical history, concomitant medications,

adverse events (AE), ECG, vital signs, laboratory results and PK/PD information will be reviewed. In addition to DLTs, all  $\geq$  grade 3 toxicities not meeting DLT criteria will be reviewed and may be considered in DLRT decisions. Modeling of available potential safety risk data (eg, for thrombocytopenia) to predict safety risk for dose escalation decisions may also be considered.

Dose escalation/de-escalation decisions will be guided by the BLRM model of dose toxicity described by [Appendix D](#). An Amgen representative will notify the sites in writing the dosing decision from the DLRM and when a cohort is open to screen new subjects.

DLTs experienced by subjects after completing the DLT period will be considered in the BLRM design to account for any late onset toxicity.

Dose escalation for each group will continue until any of the following events occur:

- The highest planned dose level is determined to be safe and tolerable (minimum of 6 evaluable subjects)
- MTDs are identified for each group where BLRM repeats the recommendation of a dose level (minimum of 6 evaluable subjects)
- The maximum of 30 evaluable subjects have been enrolled in each group. If fewer than 6 subjects are treated at the MTD/RP2D, additional subjects may be enrolled to confirm safety and tolerability.

If there are concerns about the tolerability of the current dosing schedule, alternative dosing schedules or lower dose(s) may be explored, including modification of the lead-in period dosing regimen. The alternative dose and schedule will be jointly determined by the investigators and the Amgen medical monitor, based on pharmacokinetic and safety and toxicity data.

#### **6.2.1.3 Dosage Adjustments, Delays, Rules for Withholding or Restarting, Permanent Discontinuation**

NOTE: For subjects who meet clinical or laboratory TLS per Cairo-Bishop criteria ([Appendix K](#) and [Appendix L](#)) see [Section 6.2.1.1.1](#) for dose adjustment details.

#### **Dosage Adjustments**

The subject should continue on the same dose of AMG 397 throughout the study unless the following events occur:

- For subjects experiencing an adverse event meeting the DLT definition or intolerable related adverse events BUT showing evidence of response, there will be an option to reduce the dose to the immediate next lower dose level shown to be safe and tolerable in the dose escalation part of the study.
- AMG 397 can be resumed once the adverse events recover to baseline or Grade 1 and the reintroduction of AMG 397 is deemed safe by the Investigator, Amgen's Medical Monitor, and Global Safety Officer.

**NOTE:** Subjects must be informed of the risk of continuing on therapy. Each subject is only allowed a single dose reduction.

Subjects should not be re-challenged with AMG 397 if the following AMG 397-related adverse events occur:

- Any life-threatening adverse events
- DILI (Drug Induced Liver Injury) meeting Hy's law
- Persistent grade 3 adverse events that do not recover to baseline or Grade 1 within 4 weeks of last dose
- Any treatment-related adverse event meeting DLT-criteria that recurs

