### **Rules for Restarting**

AMG 397 dosing can be resumed:

- If the toxicities resolve to grade  $\leq 1$  or return to subjects' baseline values
- Restarting of therapy is deemed safe by the investigators and Amgen's medical monitor.

Approved

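### After a life-threatening, drug-related clinical tumor lysis syndrome on lead-in dosing, one protocol rule repeats the lead-in and another bars rechallenge, and nothing lifts the ban

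*Protocol*

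**What the plan says.** **The ban.** Section 6.2.1.3, Dosage Adjustments, opens the list with "Subjects should not be re-challenged with AMG 397 if the following AMG 397-related adverse events occur". Its items include "Any life-threatening adverse events" and "Any treatment-related adverse event meeting DLT-criteria that recurs". TLS is not excepted anywhere in the list.

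**The repeat rule.** Section 6.2.1.1.1, Dose Adjustments for Lead-In Dosing, applies after lead-in dosing when one or more Cairo-Bishop criteria are met, citing Appendix K (clinical) and Appendix L (laboratory). Dosing is held until resolution. Then "Upon resolution, the subject will repeat the lead-in dosing for an additional week prior to receiving the target dose". A note adds: "Lead-in dosing will be repeated if the subject is observed to meet one or more of the Cairo-Bishop criteria post-dose". There is no grade ceiling and no cap on repeats.

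**The links between them.** A note under the heading of Section 6.2.1.3 refers subjects with clinical or laboratory TLS to Section 6.2.1.1.1 for details of dose adjustment. Under Rules for Permanent Discontinuation, the bullet on events meeting DLT criteria has two exceptions: responding subjects, and subjects with TLS, who are again sent to Section 6.2.1.1.1.

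**The concern.** The two rules lead to opposite outcomes for the same event. Under the ban, AMG 397 stops for good. Under the repeat rule, the subject has another lead-in week and then the target dose. Section 6.5.7 describes that target dose as an escalation from the lead-in dose, so a subject whose TLS arose in the lead-in week would be moving up.

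The repeat rule also asks for less agreement than the protocol requires elsewhere. For other DLTs in responding subjects, resumption must be "deemed safe by the Investigator, Amgen's Medical Monitor, and Global Safety Officer", and the discontinuation rules add that the restart is at a reduced dose. The repeat rule states neither condition.

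The risk is not remote for this class. The TLS paragraph of Section 2.2.4 reports clinical TLS with a drug of the same mechanism. The governing rule should not have to be worked out after such an event.

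**Working it through.** There is no arithmetic here. The check is whether one event satisfies both rules, and whether any other text ranks them.

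1. **Does a life-threatening clinical TLS trigger the repeat rule?** Yes. The trigger is one or more Cairo-Bishop criteria. Appendix K defines clinical TLS as laboratory TLS plus at least one clinical complication, so every clinical TLS meets the trigger whatever its grade. Grade 4 arrhythmia in Appendix K is expressly life-threatening.

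2. **Does the same event trigger the ban?** Yes, if it is judged related. Section 9.2.1 judges relatedness by whether there is a reasonable possibility that the product caused the event. The ban covers related life-threatening events of any kind.

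3. **Does the note at the head of Section 6.2.1.3 settle it?** Not expressly. It refers TLS elsewhere for how the dose is adjusted. Whether the subject may be dosed again at all is a different question.

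4. **Does the TLS exception under permanent discontinuation settle it?** No. It qualifies the bullet on DLT-level events, not the rechallenge list. The exception for responders sits beside it. If exceptions placed there lifted the ban, a responder with a related life-threatening DLT could also be re-dosed, and the ban would have little left to do.

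5. **Do the other safeguards settle it?**
   - Normal electrolytes before dosing (Section 6.2.1.1.1) and hospitalization for each extra lead-in week (Section 6.5.7) govern how dosing resumes, not whether it does.
   - Rules for Restarting require that "Restarting of therapy is deemed safe by the investigators and Amgen's medical monitor". But that rule sits in the section from which the note refers TLS away, so whether it applies is part of the same open question.
   - "Decisions to modify the AMG 397 lead-in dosing period regimen, lead-in period starting dose, and dosing increments" are for the investigator and medical monitor. That power does not say whether a barred subject may be re-dosed.
   - Section 6.4 attributes a TLS DLT in the lead-in period to that period and allows the regimen to change for later cohorts. It says nothing on rechallenging the affected subject.

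6. **Does any other text rank the rules?** No. None of the protocol text on TLS dosing, holding, restarting or rechallenge (Synopsis, Figure 2, Sections 3.1, 6.2.1.1.1, 6.2.1.2, 6.2.1.3, 6.4 and 6.5.7) does so. The SAP has no rechallenge rule.

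The Amendment 1 change description marks the note and the TLS exception as additions and shows the rechallenge list unmarked. That fits a TLS pathway written around an existing ban without the two being reconciled.

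**The case against.** The strongest answer is that the specific rule displaces the general one. The note names clinical TLS. The ban is printed under Dosage Adjustments, and the destination text is headed as dose adjustments for lead-in. On that reading the note removes TLS from the whole sub-section, ban included. This has force as a guide to the intended pathway for TLS in general. It does not carry a prohibition on rechallenge after a life-threatening event, which no sentence lifts.

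Further points narrow the concern:

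- Two other grounds for permanent discontinuation, intolerability of treatment and clinically significant deterioration of health status, carry no TLS exception and could reach a life-threatening TLS. They are a partial backstop that depends on judgment.
- Section 8.2 lets the investigator or sponsor withdraw a subject at any time. The sponsor must hear of any Grade 3 or higher event within 24 hours (Section 6.2.1.1), so a site would not be deciding alone.
- An Appendix K footnote marks the listed complications as not directly or probably attributable to the therapeutic agent. That clouds which clinical TLS events count as drug-related and shrinks the overlap.

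A reader might infer that recurrence raises the same problem, since any clinical TLS is a DLT (Section 6.4) and the list also bars "Any treatment-related adverse event meeting DLT-criteria that recurs". The documents do not support pressing that as far. The lead-in note and Section 6.5.7 foresee repeated lead-in weeks, and the note and exception in Section 6.2.1.3 favour that route. An automatic ban would also catch a second mild episode: Appendix K grade 1 creatinine is 1.5 times the upper limit of normal. That is a clinical trade-off for the sponsor.

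**Conclusion.** The point holds for one case: a subject on lead-in dosing with an AMG 397-related clinical TLS that is life-threatening and resolves. The repeat rule followed as written returns that subject to the target dose; the rechallenge list followed as written does not. The cross-references favour repeat lead-in for laboratory TLS and for clinical TLS that is not life-threatening, including recurrent episodes, but they do not lift the ban for life-threatening events.

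A reader might infer that the protocol orders re-dosing after life-threatening TLS, or gives no direction on TLS at all. Neither is right: this is unresolved precedence, and the protocol does route TLS to the lead-in section. A first TLS before lead-in is also outside the point, because Section 6.2.1.1.1 says only that lead-in may then be started.

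This is a minor safety clarification. The documents give no TLS rate, so no count can be computed, but the conditions that must coincide make it likely that few subjects are affected. The conclusion assumes that the event is judged drug-related despite the Appendix K footnote. It also rests on the Amendment 1 protocol text. The SAP follows Amendment 4 and reports Part 1 closed with 24 subjects enrolled. It keeps lead-in wording in its DLT observation period, but whether the dosing rules were later reconciled cannot be seen.

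**What to change.** Add to Section 6.2.1.1.1, Dose Adjustments for Lead-In Dosing: *Repeat lead-in dosing does not apply after AMG 397-related clinical TLS that is life-threatening; the rechallenge ban in Section 6.2.1.3 governs.*

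Add to the note at the head of Section 6.2.1.3 and to the TLS exception under Rules for Permanent Discontinuation: *subject to the rechallenge ban for life-threatening events.*

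For recurrent clinical TLS that is not life-threatening, leave the choice to the sponsor and impose no automatic ban.

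The cost is one sentence and two short insertions. The downside is that the rare subject whose life-threatening TLS has resolved can no longer receive AMG 397.
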